301 surveillance or clinician-led surveillance. Participants will be sent questionnaires at six months to
302 measure outcomes using paper or online surveys. We will also collect data through the web-based
303 version of the ASICA skin checker (in the intervention group), patient diaries (to measure out of
304 pocket costs), and from the clinic databases (including follow-up visits, surgical procedures and
305 pathology reports of any skin lesions removed).

306 6. Study design

307 6.1. Research question(s)/ aim(s):

308 The **primary aim** of the study is to investigate whether patient-led surveillance (Web-based version
309 of the ASICA skin checker + smartphone App and dermatoscope attachment + Teledermatology +
310 email/SMS reminders) is feasible.

311 The **secondary aims** are to investigate whether patient-led surveillance:

- 312 1. increases patients' adherence with recommended SSE practice (total body self-examination
313 conducted two- monthly)
- 314 2. improves confidence in, knowledge of, attitudes and beliefs about, skin self-examination,
- 315 3. decreases level of fear of new or recurrent melanoma, general anxiety, stress and
316 depression,

- 317 4. decreases the number of lesions surgically excised, the number of follow up visits attended
318 (both scheduled and unscheduled), resource use and costs and carbon emissions (costing
319 study)
320 5. Increases acceptability of reducing scheduled clinic visit frequency
321 6. has acceptable inter-rater reliability for the Teledermatology assessment (reliability sub-
322 study)
323 7. is accepted by clinicians and patients views (qualitative sub-study)
324

325 6.2. Study design

326 This study is a 2-armed RCT with 1:1 allocation to intervention vs the control group, with a
327 Teledermatology repeatability sub-study nested within the intervention arm to estimate the inter-
328 rater reliability of Teledermatology.
329

330 In addition, we will conduct a costing study to estimate the total costs to the health system, to
331 patients, and to the planet (carbon emissions) for the intervention and control groups. All costs
332 associated with SSE, skin surveillance and management of newly identified lesions, out-of-pocket
333 costs and opportunity costs will be included. We will also measure and value all resources used
334 (micro-costing approach) to estimate the carbon emissions associated with melanoma surveillance
335 for the intervention and control groups.

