336 We will conduct a qualitative sub-study to understand patients' and clinicians' acceptability and
337 satisfaction with the intervention and explore components which may need to be changed. The
338 qualitative evaluation will be in the form of phone or face to face interviews at the end of the 6
339 month follow-up.
340

341 7. Study population

342 We will recruit adult participants who have been treated for a first primary melanoma, stage 0/I/II,
343 and who are undergoing regular melanoma follow-up at recruiting melanoma and skin cancer
344 clinics in NSW.
345

346 This pilot study aims to recruit 100 patients from the Melanoma Institute Australia (MIA) and Royal
347 Prince Alfred Hospital (RPAH) (specialist treatment centres) and the Newcastle Skin Check clinic
348 (GP run clinic). Recruitment will be done over six months.
349

350 7.1. Inclusion Criteria

- 351 • Patients treated for stage 0/I/II melanoma who are attending regular melanoma follow-up as
352 indicated by scheduled or recommended visit within next 12 months.
353 • Are able to self-examine;
354 • Have a suitable study partner (spouse, partner, family member, friend) to help with self-
355 examination
356 • Own a compatible Smartphone (and have access to Wifi / email / SMS text messaging);
357 • Are able to give informed consent;
358 • Have sufficient English language skills to read the materials and complete the
359 questionnaires;
360 • Aged 18+ years old.

361 7.2. Exclusion Criteria

- 362 • unable to perform self-examination
363 • Patient who currently or previously have had stage III/IV melanoma
364 • Patients with a known past or current diagnosis of cognitive impairment

365 8. Study procedures

366 8.1. Enrolment procedure

367 All patients treated for localised melanoma who are attending regular follow-up, will be identified in
368 clinic by the clinician. The potential participant will be contacted by a research coordinator who will
369 explain the study and give the patient an invitation package either in person or by mail. The initial
370 study invitation package includes: Study Invitation Letter, Participant Information Sheet, Consent
371 Form, Participation Card, Baseline Questionnaire (to measure demographics, knowledge, attitudes
372 and confidence on self-examination and smartphone Apps, and their baseline level of fear of new
373 or recurrent melanoma (using a melanoma specific version of the Fear of Cancer Recurrence

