8.6. Asses

464 **ment schedule and follow up**

465 *Follow-up:* All participants will be complete a questionnaire at baseline (T0: prior to randomisation)
466 and 6 months (T1) follow-up which they can complete in hard copy or online. Data will be extracted
467 from clinic databases for 6 months from randomisation, including surgical procedures and
468 histopathology.

469 **8.6.1. Follow-up questionnaire (T1): 6 months**

470 Participants will be mailed the first follow-up questionnaire (or provided with a link to the online
471 survey via email) 6 months after randomisation. If participants do not return their completed
472 questionnaire within 1 week of postage or email, the researchers will contact the participant by
473 SMS text and/or email (according to the participant's preferred method of contact) as a reminder
474 about the study. The researchers will remind the participant 5 times. If there are delays with the
475 return of the questionnaire, and the participant appears to have problems completing the
476 questionnaire on paper or online, the research coordinator will offer to administer the questionnaire
477 over the telephone.
478

479 **8.6.2. End of study.**

480 Measurement of outcomes will be at 6 months (T1questionnaire) for evaluation of intervention
481 effects. If a patient has not completed the schedule of follow up visits, further follow up of outcomes
482 will continue up to a maximum of 12 months. If a patient withdraws consent to participate, a Study
483 Discontinuation Form will be completed (see below).
484

485 Similarly, if a patient dies, a Study Discontinuation Form will be completed and a copy of the death
486 certificate or discharge summary provided. Reason for death, melanoma/skin cancer related or not,
487 will be considered in the final analysis.
488

489 **8.6.3. Withdrawal and Lost to Follow up**

490 Participation in this study is voluntary; patients are able to withdraw at any time.
491

492 If a patient decides to stop their follow-up visits but is willing to keep in contact via telephone, their
493 health status will be periodically ascertained by way of phone contact with their general practitioner
494 or by direct phone contact with the patient.
495

496 For those patients who want to have no further contact, all correspondence regarding the trial will
497 be discontinued. A Study Discontinuation Form is to be completed at the last study visit the patient

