637 M2.1. *Adherence with recommended SSE practice* (total body self-examination conducted two-
 638 monthly); Participants will be asked how often they perform a complete examination of their skin.
 639 M2.2. *Thoroughness, confidence, beliefs, attitude, and knowledge of SSE* will be assessed by
 640 items adapted from Janda et al.

641 **(M3) Level of fear of new or recurrent melanoma (FCR) severity:** FCR will be assessed using a
 642 modified (i.e. melanoma-specific) version of the 9 item Fear of Cancer Recurrence Inventory (FCRI)
 643 severity subscale, the most comprehensive multi-dimensional scale of FCR available.⁷ A higher
 644 score is indicative of greater FCR.

645 **(M4) General anxiety, stress and depression:** Anxiety, stress and depression will be measured
646 using the short version of the Depression Anxiety and Stress Scales (DASS-21).¹⁷ The DASS-21 is
647 a set of three 7-item self-report scales designed to measure the emotional states of depression,
648 anxiety and stress. The depression scale measures dysphoria, hopelessness, devaluation of life,
649 self-deprecation, lack of interest/involvement, anhedonia and inertia. The anxiety scale measures
650 autonomic arousal, skeletal muscle effects, situational anxiety, and subjective experience of
651 anxious affect. The stress scale assesses difficulty relaxing, nervous arousal, and feeling irritable
652 and impatient.

653 **(M5) Acceptability of reducing scheduled clinic visit frequency:** will be measured through
654 item(s) designed specifically for this questionnaire.

655 **(M5) Number of lesions surgically evaluated;**

656 **(M6) Number of clinic visits attended** (both scheduled and unscheduled)

657 **(M7) Inter-rater reliability for the Teledermatology assessment:** We will carry out a repeatability
658 study after trial close-out where the three study dermatologists independently report on cases they
659 did not provide teledermatology assessment for during the trial. We will compare results across the
660 three dermatologists to assess agreement.

661 **(M8) Resource use:** Patient out of pocket and health system costs associated with each arm of the
662 trial will be estimated using a resource use diary. The diary will be used to document and measure
663 health behaviours and service use - such as hospitalisation, other allied health consultations, use of
664 alternative therapies and self-monitoring behaviours. The diary will also document days out-of-role

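### The DASS-21 and self-examination frequency and thoroughness are not stated to be collected at baseline, and the planned 6-month comparisons use no baseline values: a loss of precision, not of validity

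*Combined protocol and SAP*

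**What the plan says.** **Baseline content.** Section 8.1 describes the invitation package and, in a parenthesis, what the baseline form measures: "Form, Participation Card, Baseline Questionnaire (to measure demographics, knowledge, attitudes", continuing "and confidence on self-examination and smartphone Apps, and their baseline level of fear of new" or recurrent melanoma, with the fear instrument named.

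**Timing.** Section 8.6 says "All participants will be complete a questionnaire at baseline (T0: prior to randomisation" and again at 6 months, without listing the items of either form. The schedule of assessments in the appendix also lists the questionnaires without their content. Section 8.6.2 adds: "Measurement of outcomes will be at 6 months (T1questionnaire) for evaluation of intervention" effects.

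**Outcomes without a time point.** Section 12.2 gives no assessment times for two of the patient-reported measures at issue:
- M2.1, adherence to two-monthly total-body examination: "Participants will be asked how often they perform a complete examination of their skin".
- M4, general anxiety, stress and depression, measured "using the short version of the Depression Anxiety and Stress Scales (DASS-21".

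M2.2 adds thoroughness, confidence, beliefs, attitude and knowledge, also without times.

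**Aims.** Section 6.1 asks whether patient-led surveillance "increases patients' adherence with recommended SSE practice (total body self-examination" every two months (aim 1), and whether it "decreases level of fear of new or recurrent melanoma, general anxiety, stress and" depression (aim 3).

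**Analysis.** Section 13.4.2 plans a chi-squared test for regular self-examination and a t-test for fear at 6 months. It reports estimates with confidence intervals and acknowledges limited power. It mentions no baseline covariate and no analysis of the DASS-21.

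**The concern.** Aim 1 and part of aim 3 are worded as an increase and a decrease, yet nothing in the protocol says that the corresponding measures are taken before randomisation. M10 in section 12.3 records a personal history of depression or anxiety, but that is not a score on the outcome scale.

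Four things are at stake.
- **Precision.** With 50 per arm and power conceded to be limited, interval width is what these analyses deliver. A baseline value of the same measure is usually the best covariate for reducing it.
- **Balance.** Prior self-examination varies: section 5.1 cites less than half of respondents in one study, and 14% in another, examining all parts of the body. Neither prior self-examination nor distress is a stratification factor in section 8.2, so a chance imbalance could be neither seen nor adjusted for.
- **Planning the larger trial.** Section 5.2 says that trial will aim for better psychological outcomes. A pilot without baseline DASS-21 scores cannot estimate the baseline to 6-month correlation needed to size a baseline-adjusted comparison.
- **Missing data.** Section 13.6 leaves imputation open. A baseline value of the same measure would be a natural predictor.

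**Working it through.** **Step 1: the sections side by side**

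| Measure | Stated at baseline (8.1)? | Analysis in 13.4.2 |
|---|---|---|
| Fear (M3) | Yes | t-test at 6 months, unadjusted |
| Knowledge, attitudes, confidence (M2.2) | Yes | None given |
| Thoroughness (M2.2) | No | None given |
| Self-examination frequency (M2.1) | No | Chi-squared test, unadjusted |
| DASS-21 (M4) | No | None given |

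Two separate gaps follow. The baseline content is incomplete or incompletely described, and no baseline value is used in any analysis, not even the fear score that is collected.

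**Step 2: the plan's own precision figure**

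The only precision figure is in section 13.1 and concerns the primary outcome: a margin of error below 10% with 100 participants and 30% recruited.
- Wald half-width: 1.96 × √(0.30 × 0.70 / 100) = 0.0898.
- Wilson interval, the method named in 13.4.1: 21.9% to 39.6%.
- With contacted patients as denominator (100 / 0.30 ≈ 333), the Wald half-width is 0.049.

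The figure reproduces and does not depend on the present point. The plan gives no precision figure for the secondary outcomes.

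**Step 3: inputs for the secondary outcomes**
- 50 per arm (synopsis and section 13.1).
- Baseline to 6-month correlation r: not in the documents. Assumed 0.3 to 0.7 for continuous scores and 0.3 to 0.5 for binary adherence.
- Standard deviation and drop-out: not in the documents. Results are in SD units and assume no drop-out unless stated.

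**Step 4: continuous scores (DASS-21 scales, fear)**

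Unadjusted 95% half-width = t(0.975; 98 df) × √(2/50) = 1.984 × 0.2 = 0.397 SD. ANCOVA multiplies the residual SD by √(1 − r²) and costs one degree of freedom. The equivalent sample size is 50 / (1 − r²) per arm.

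| r | 1 − r² | Half-width (SD) | Narrower by | Equivalent per arm |
|---|---|---|---|---|
| none | 1 | 0.397 | – | 50 |
| 0.3 | 0.91 | 0.379 | 4.6% | 55 |
| 0.5 | 0.75 | 0.344 | 13.4% | 67 |
| 0.7 | 0.51 | 0.283 | 28.6% | 98 |

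If only 40 per arm returned the 6-month form (an assumption), the half-width would be 0.445 SD unadjusted and 0.386 SD at r = 0.5. The relative gain is the same.

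**Step 5: binary adherence**

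For a risk difference standardised over a binary baseline, the same factor √(1 − r²) is an approximation, with r the within-arm correlation. It gives 4.6% at 0.3 and 13.4% at 0.5. As an illustration, take assumed adherence of 30% and 50%. The unadjusted half-width is 1.96 × √(0.30 × 0.70/50 + 0.50 × 0.50/50) = 0.188. It becomes 0.188 × 0.954 = 0.179 at r = 0.3 and 0.188 × 0.866 = 0.163 at r = 0.5. The gain is smaller than for the scores only because the assumed correlations are lower.

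**The case against.** The strongest reply is that absence is being inferred from a short descriptive parenthesis. The questionnaire itself is not in the documents, and the parenthesis may well be abbreviated. It omits the history of depression or anxiety listed in M10, and it names three of the five constructs in M2.2, leaving out beliefs as well as thoroughness. This stands. A reader might infer that the sponsor decided not to measure these at baseline, but the documents support only that their collection is not stated.

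Other stronger readings also go too far.
- **That two secondary aims have no baseline.** Aim 3 begins with fear, which has an explicit one. Only its anxiety, stress and depression part is affected, together with aim 1.
- **That the aims cannot be answered.** They can be read as contrasts between randomised arms. Such a contrast at 6 months is valid without baseline values, and its confidence interval already allows for chance imbalance.
- **That the equivalent of 67 to 98 per arm applies to adherence.** Those figures are for linear adjustment of a continuous score. Covariate adjustment in a logistic model targets a conditional odds ratio and does not shrink the variance of the log odds ratio by 1 − r².
- **That adding items is enough.** Fear has a baseline and is still to be compared unadjusted, so new items alone would gain no precision under 13.4.2.

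A further objection concerns cost. Section 8.2 makes receipt of the baseline form a condition of randomisation, and the primary outcome is the proportion of invited patients who are randomised. A longer form could therefore touch the primary outcome. This also stands and belongs in the decision, although the added burden is modest.

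**Conclusion.** The point holds as a gap in what is stated and in what is analysed. No section says that the DASS-21, self-examination frequency or thoroughness is collected at baseline, and section 13.4.2 uses no baseline value and gives no DASS-21 analysis. The randomised comparisons remain valid. The loss is in precision, in checking balance and in describing change.

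The size rests entirely on correlations that the documents do not give. At the low end the gain is slight, and at the high end it is close to doubling the sample for the continuous scores. For adherence it could fall to the low end or below if the intervention moves most participants to regular examination, because baseline habit would then predict little in that arm.

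Priority is minor. These are secondary outcomes in a feasibility pilot that already concedes limited power, and the primary estimate and sample size do not depend on them.

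**What to change.** 1. **Section 8.1 (and the schedule of assessments):** itemise the baseline questionnaire. Include the DASS-21 and the M2 items on frequency and thoroughness. If the form already holds them, correct the list.
2. **Section 12.2:** give the assessment times for M2 and M4.
3. **Section 13.4.2:** analyse each 6-month DASS-21 scale by ANCOVA on its baseline score, and fear in the same way. Analyse two-monthly adherence as a risk difference standardised over baseline adherence. Report each with a 95% confidence interval.
4. **For the larger trial:** report the observed baseline to 6-month correlations.

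**Cost.** If the items are not yet on the form, it grows by 21 DASS-21 items (three 7-item scales) plus a few self-examination items, whose number the documents do not give. The form is already sent and must be back before randomisation, so the values would be unaffected by allocation. For the same reason, a longer form could slightly lower the recruitment proportion. As an illustration, a fall from 30% to 29% would raise the contacts needed for 100 participants from about 333 to about 345 (100 / 0.29). The sponsor should state that it accepts this. Adjusting for the fear baseline costs nothing, since that score is already planned.

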8.6. Asses

464 **ment schedule and follow up**

465 *Follow-up:* All participants will be complete a questionnaire at baseline (T0: prior to randomisation)
466 and 6 months (T1) follow-up which they can complete in hard copy or online. Data will be extracted
467 from clinic databases for 6 months from randomisation, including surgical procedures and
468 histopathology.

469 **8.6.1. Follow-up questionnaire (T1): 6 months**

470 Participants will be mailed the first follow-up questionnaire (or provided with a link to the online
471 survey via email) 6 months after randomisation. If participants do not return their completed
472 questionnaire within 1 week of postage or email, the researchers will contact the participant by
473 SMS text and/or email (according to the participant's preferred method of contact) as a reminder
474 about the study. The researchers will remind the participant 5 times. If there are delays with the
475 return of the questionnaire, and the participant appears to have problems completing the
476 questionnaire on paper or online, the research coordinator will offer to administer the questionnaire
477 over the telephone.
478

479 **8.6.2. End of study.**

480 Measurement of outcomes will be at 6 months (T1questionnaire) for evaluation of intervention
481 effects. If a patient has not completed the schedule of follow up visits, further follow up of outcomes
482 will continue up to a maximum of 12 months. If a patient withdraws consent to participate, a Study
483 Discontinuation Form will be completed (see below).
484

485 Similarly, if a patient dies, a Study Discontinuation Form will be completed and a copy of the death
486 certificate or discharge summary provided. Reason for death, melanoma/skin cancer related or not,
487 will be considered in the final analysis.
488

489 **8.6.3. Withdrawal and Lost to Follow up**

490 Participation in this study is voluntary; patients are able to withdraw at any time.
491

492 If a patient decides to stop their follow-up visits but is willing to keep in contact via telephone, their
493 health status will be periodically ascertained by way of phone contact with their general practitioner
494 or by direct phone contact with the patient.
495

496 For those patients who want to have no further contact, all correspondence regarding the trial will
497 be discontinued. A Study Discontinuation Form is to be completed at the last study visit the patient
498 attends and this is to be submitted to the Trial Coordinating Centre.
499

500 The National Death Index at the Australian Institute of Health and Welfare and other local
501 databases, including clinic databases, may be used to collect outcome information on patients who
502 have been lost to follow-up.

503 **9. Data Collection**

504 Trial data will be recorded in full on the CRFs (hardcopy to each site) or eCRFs (eDatabase).
505

506 The site is required to complete all appropriate data entry fields as specified on the forms. The
507 investigator will be asked to confirm the accuracy of completed CRFs by signing forms as indicated.
508 Source documents pertaining to the trial must be maintained by investigational sites. Source
509 documents may include a subject's medical records, hospital charts, operation reports, the
510 investigator's subject study files, as well as the results of diagnostic tests such as laboratory and
511 pathology results.
512

513 The Trial Management Centre (TMC) may request copies of some source documents in support of
514 the CRF as a quality assurance exercise. All study-related documentation is required to be
515 maintained by the site for 15 years following completion of the study.

516 10. Intervention

517 10.1. Intervention and comparison arms

518 The intervention comprises:

- 519 • **The web-based ASICA (Achieving Self-directed Integrated Cancer Aftercare) Skin-**
520 **Checker** is used to record regular Skin Self-Examination.¹⁵ The patient will be prompted to
521 perform a skin exam every two months. When the patient discovers a skin change or lesion,
522 the patient will report the changes on the web-based ASICA survey. The skin report
523 contains a description of the change or lesion and where it is located. Participants are
524 required to provide text reports on each part of the body before they can proceed with
525 submitting the report through the site (if there are no concerning changes/lesions then this is
526 reported for each part of the body).
- 527 • **Dermatoscope and Teledermatology:** Smartphone App and dermatoscope that can be
528 attached to a smartphone for patients to use. The device allows magnified images of skin
529 lesions to be taken under polarized light for electronic transmission to a specialist. This store
530 and forward process is called “mobile teledermatology”. Three dermatologists will be
531 rostered on to review the reports and images of patient detected lesions, and feedback
532 recommendations to the patient as to the action that needs to be taken. They will report
533 results within 3 working days of receiving the electronic text report and images from the
534 patient. If the report is not reviewed in this timeframe the site study coordinator will notify the
535 patient of a delay in reporting. They will provide one of the following recommendations:
 - 536 ○ Follow Up Photo - There is no immediate concern today, but this case should
537 continue to be monitored. Please take another picture and resubmit for review.
 - 538 ○ Retake Photo - Unfortunately, the image quality is not sufficient for
539 teledermatology review. Please retake the photo.
 - 540 ○ Clinical Exam - We recommend that you book an appointment with your doctor
541 to examine this case. Please call your melanoma clinic to make an appointment
542 at your earliest convenience.
 - 543 ○ No Concern Today - This case does not seem to be suspicious at this time. Self-
544 monitor and review with your doctor at your next scheduled visit.
 - 545 ○ Biopsy/Excision - We recommend that you book an appointment with your doctor
546 to examine this case as biopsy or excision may be needed. Please call your
547 melanoma clinic to make an appointment at your earliest convenience.
 - 548 ○ Other
- 549 • Educational booklet ‘Your guide to early melanoma’: The freely available booklet developed
550 by the Melanoma Institute Australia for patient support and comprises a treatment-
551 management organiser and detailed information source in one booklet. Contents include: -
552 Diagnosis summary - Melanoma glossary - Treatment plan - Pain diary - Medication chart -
553 Body maps for self-examination - Frequently asked questions - Supportive services -
554 Information on treatments and surgical procedures
- 555 • Written and video instructions on how to use the dermatoscope + Smartphone App
- 556 • Email and/or SMS text reminders every 2 months to perform self-examination
- 557 • Unscheduled visits as needed in addition to those prompted through Teledermatology
- 558 • Scheduled visits as needed
- 559 • Monthly diaries capturing clinic visits and travel costs

560

561 The control arm comprises

- 562 • An educational booklet ‘Your guide to early melanoma’;
- 563 • Unscheduled visits as needed

- 564 • Scheduled visits as needed
565 • Monthly diaries capturing clinic visits and travel costs
566

567 **10.2. Intervention/ treatment modification**

568 Participation in this study does not stop participants in either the intervention or control groups from
569 seeking professional medical care. Access to formal health services will, however, be recorded as
570 part of the study.

571 **10.3. Distribution, packaging and labelling**

572 The initial Invitation letter will be sent on clinician letterhead to the participant at the address on file
573 at the clinic database. Following consent and receipt of the baseline study questionnaire, the study
574 packages will be distributed by the research coordinator, according to their random intervention or
575 control group allocation, to participants through the mail or during their routine clinic visit (as
576 directed by participant preference).

577 **10.4. Accountability for intervention**

578 It is the responsibility of the research coordinator to make sure that all participants receive their
579 packages according to their randomised group allocation.

580 **11. Safety Reporting**

581 **11.1. Adverse Events**

582 An Adverse Event (AE) can be any unfavourable and unintended sign, symptom, or disease
583 temporally associated with the use of an intervention, whether or not related to the intervention.

584
585 In cases of surgical or diagnostic procedures, the condition/illness leading to such a procedure is
586 considered as the AE rather than the procedure itself.

587

588 Medical device adverse event / incident:

- 589 • An event associated (caused or partially attributable) with the use (or misuse) of a
590 medical device.
591 • An event that resulted in or could have resulted in (had effective intervention not taken
592 place) serious injury, illness or death to patient, healthcare worker or other person.
593 • Faults that may affect the quality of device, timeliness of assessment and cost-
594 effectiveness such as, problems with getting the device to operate, repeated repairs,
595 device design and difficulty of use.
596

597 All AEs with the smartphone App and dermatoscope will be recorded and reviewed by the trial
598 management committee.
599

600 **11.2. Serious Adverse Events**

601 **SAE Definitions**

602 A serious adverse event (SAE) is any untoward medical occurrence which:

- 603 • is fatal;
604 • is life-threatening;
605 • requires unanticipated in-patient hospitalisation or prolongation of hospitalisation;
606 • results in persistent or significant disability or incapacity;
607 • is a congenital anomaly/birth defect;
608 • is a grade 4 (NCI CTCAE v4.0) toxicity;

609 **and**

- 610 • could be related to the device and/or software
 611 The term “life threatening” in the definition of SAE refers to an event in which the participant was at
 612 risk of death at the time of the event; it does not refer to an event which, hypothetically, might have
 613 caused death if it were more severe.

614

615 **SAE Reporting**

616 All relevant and subsequent information relating to each reported SAE must be submitted on the
 617 CRF, along with any available source documentation, to the Trial Coordinating Centre. This must
 618 be completed within 24 hours of the site becoming aware of the event and all SAE CRFs require
 619 the signature of the Principal Investigator.

620

621 **SAE Reporting Timelines**

Type	Timeframe
Initial SAE Report	The site must submit the original SAE Form to the Trial Coordinating Centre within 24 hours of becoming aware of a trial participant experiencing an SAE. Please provide copies of relevant source documents if available. Should the site have any questions please immediately contact the Trial Coordinating Centre for assistance.
Updated Report	The site should provide any updates to the Trial Coordinating Centre as soon as possible. Please use the original SAE Form, and use additional Forms if more space is required. Please provide copies of all relevant source documents if available.
Completed Report	Once the event has resolved or if the participant has died, using the original SAE Form(s), the site should provide the complete report to the Trial Coordinating Centre as soon as possible. This must include relevant source documents.

622

623 All SAEs will be reviewed by the Study Chair and also summarised for review by the Data Safety
 624 Management Committee.

625

626 SAEs will be reported as per the local Ethics Committee (EC)/Research Governance Officer (RGO), in
 627 accordance with international and local laws and regulations.

628

629 Should any trial site have any questions they will immediately contact the Trial Coordinating Centre for
 630 assistance.

631 **12. Outcomes/ Measures**632 **12.1. Primary outcome**

633 **(M1)** The primary outcome is the **proportion of patients who are invited to participate who are**
 634 **finally randomised into the trial.**

635 **12.2. Secondary outcomes**636 **(M2) Skin –Self Examination (SSE) including:**

637 M2.1. *Adherence with recommended SSE practice* (total body self-examination conducted two-
 638 monthly); Participants will be asked how often they perform a complete examination of their skin.
 639 M2.2. *Thoroughness, confidence, beliefs, attitude, and knowledge of SSE* will be assessed by
 640 items adapted from Janda et al.

641 **(M3) Level of fear of new or recurrent melanoma (FCR) severity:** FCR will be assessed using a
 642 modified (i.e. melanoma-specific) version of the 9 item Fear of Cancer Recurrence Inventory (FCRI)
 643 severity subscale, the most comprehensive multi-dimensional scale of FCR available.⁷ A higher
 644 score is indicative of greater FCR.

645 **(M4) General anxiety, stress and depression:** Anxiety, stress and depression will be measured
646 using the short version of the Depression Anxiety and Stress Scales (DASS-21).¹⁷ The DASS-21 is
647 a set of three 7-item self-report scales designed to measure the emotional states of depression,
648 anxiety and stress. The depression scale measures dysphoria, hopelessness, devaluation of life,
649 self-deprecation, lack of interest/involvement, anhedonia and inertia. The anxiety scale measures
650 autonomic arousal, skeletal muscle effects, situational anxiety, and subjective experience of
651 anxious affect. The stress scale assesses difficulty relaxing, nervous arousal, and feeling irritable
652 and impatient.

653 **(M5) Acceptability of reducing scheduled clinic visit frequency:** will be measured through
654 item(s) designed specifically for this questionnaire.

655 **(M5) Number of lesions surgically evaluated;**

656 **(M6) Number of clinic visits attended** (both scheduled and unscheduled)

657 **(M7) Inter-rater reliability for the Teledermatology assessment:** We will carry out a repeatability
658 study after trial close-out where the three study dermatologists independently report on cases they
659 did not provide teledermatology assessment for during the trial. We will compare results across the
660 three dermatologists to assess agreement.

661 **(M8) Resource use:** Patient out of pocket and health system costs associated with each arm of the
662 trial will be estimated using a resource use diary. The diary will be used to document and measure
663 health behaviours and service use - such as hospitalisation, other allied health consultations, use of
664 alternative therapies and self-monitoring behaviours. The diary will also document days out-of-role
665 (including paid and unpaid work), travel costs and carer costs. The diary will be based on existing
666 resource use questionnaires resource use recorded in databases.

667 **(M9) Qualitative results:** We will carry out face-to-face or telephone interviews with a sub-set of
668 intervention group participants at 6 months after randomisation to explore in depth patients'
669 experiences with digitally supported self-examination. We will also interview clinicians to explore
670 their experience of the benefits and limitations of the intervention.

671 **12.3. Potential confounders and biases**

672 **(M10) Demographic and other risk factors including:**

673 Age, sex, ethnicity, Indigenous status, language spoken, marital status, children, occupation,
674 income, highest education level, postcode/SEIFA, brand of smartphone owned (if applicable),
675 baseline use of digital technology/ internet, and personal history of depression or anxiety. We will
676 collect these data using standardised items from the Australian Census questionnaire and other
677 instruments, where appropriate.

678 Clinical characteristics of the index melanoma including AJCC sub-stage and site, retrieved from
679 administrative datasets at the clinics.

680 **13. Statistical methods**

681 **13.1. Sample size and justification**

682 A sample size of 100 participants, with 1:1 allocation to intervention vs control groups, will ensure
683 that the 95% confidence interval for the proportion of potential participants who are recruited has a
684 margin of error of <10% (assuming that 30% of contacted, eligible participants are recruited).

685
686 A sample size of 30 participants in the qualitative sub-study is a well-accepted sample size in
687 qualitative studies using in-depth interviews.¹⁸
688

689 **13.2. Feasibility**

690 Administrative data from our main clinic (MIA) indicates that approximately 800-900 patients are
691 treated for localised melanoma at MIA each year and approximately 50% then attend regular
692 follow-up at MIA.¹⁹ Recruiting 100 patients over 6 months from all patients treated for localised
693 melanoma who are attending follow-up at MIA and the clinic in Newcastle, is highly feasible.

694

695 13.3. Early stopping

696 There are no safety endpoints or criteria for early study termination.

697

698 13.4. Analyses plan**699 13.4.1. Statistical analysis for primary endpoint**

700 The proportion of patients who are randomised into the trial will be estimated using the number of
701 contacted patients as the denominator. The Wilson (score) method will be used to estimate the
702 confidence interval for this proportion to assess the best and worst case scenarios supported by the
703 pilot study data. We will investigate and describe any groups that had low participation rates in our
704 pilot study.

705

706

707 13.4.2. Statistical analysis for secondary endpoints

708 We will use a chi-squared test to investigate the difference in proportion undertaking regular skin
709 self-examination between the intervention arm and the usual care arm. A t-test will be used to
710 compare fear of new or recurrent melanoma severity at 6 months between the intervention and
711 usual care group. We will report any estimated differences (either proportions or means) with
712 appropriate confidence intervals as the power for these comparisons will be limited.

713

714 13.5. Secondary analyses**715 *Teledermatology Repeatability Study***

716 Sub-study to assess Dermatologist diagnostic agreement of electronic text reports and images
717 collected during the trial.

718 We will assess inter-rater agreement across three dermatologists, reporting on prospectively
719 collected Teledermatology materials. After close-out of the trial, three dermatologists (CIs [name],
720 [name] and [name]) will independently review all electronic reports and images of patient detected
721 lesions that they did not report on during the trial. All three dermatologists will report their results
722 blinded to those of the other two dermatologists and to any other clinical information apart from that
723 received during the Teledermatology (age and sex of patient and the text report describing the
724 lesion where this was provided).

725 Agreement across the following broad clinical diagnostic categories will be calculated:

- 726 • No concern today [i.e. benign]
- 727 • Follow up photo [i.e. low probability of melanoma/NMSC]
- 728 • Clinical Exam [i.e. intermediate probability of melanoma/NMSC]
- 729 • Biopsy/excision [i.e. high probability of melanoma/NMSC]
- 730 • Only one category per patient episode allowed, where teledermatologist makes more than
731 one diagnosis, most severe diagnostic category used.

732 We will construct cross-classification tables to separately compare inter-rater reliability for text
